## 7.1 Exposures

As there is no untreated comparator group, each patient included in the study is planned to be continually exposed to nintedanib as a standard of care for the whole observational period of 52 weeks at the indicated dosage of 150 mg twice daily. As this is a real-world observational study, patients will be instructed on the correct drug application by their treating physician. A dose interruption of nintedanib for more than 12 weeks and/or initiation of another antifibrotic therapy during the observation phase of the study will result in exclusion of the concerned patients' data from efficacy analysis.

Exposure variables will be cough score and symptoms score as measured via L-PF questionnaire.

## 7.2 Outcomes

### 7.2.1 Primary outcomes

- Correlation between change from baseline to week 52 in FVC [% pred.] and change from baseline to week 52 in dyspnea symptom score
- Correlation between change from baseline to week 52 in FVC [% pred.] and change from baseline to week 52 in cough symptom score

[figure not shown]
The primary outcomes do not touch any safety question.

### 7.2.2 Secondary outcomes

- Correlation between change from baseline to week 52 in FVC [mL] and change from baseline to week 52 in dyspnea symptom score; safety issue: no
- Correlation between change from baseline to week 52 in FVC [mL] and change from baseline to week 52 in cough symptom score; safety issue: no
- Absolute change from baseline in L-PF cough symptom score [points] at week 52; safety issue: no
- Absolute change from baseline in L-PF dyspnea symptom score [points] at week 52; safety issue: no

Primary and secondary outcomes will be analyzed for the Treated Set.

The secondary outcomes do not touch any safety question.

**7.3 Covariates**

Covariates for adjustment will include the following disease characteristics:

- Pulmonary function test (DLCO) result [% pred] at baseline
- FVC result [% pred.] at baseline
- FVC result [mL] at baseline

**8. DATA SOURCES**

Medical records collected through routine clinical care will be used to assess the inclusion/exclusion criteria of patients as well as for patient demographics, smoking history, collection of previous ILD medication, concomitant diseases, and concomitant medication, as well as for the health data of the patient during the course of the observation. The L-PF questionnaire will be provided as paper version to the patient to be filled out in writing at visits V1 to V5, as applicable.

No further data sources are needed for statistical analysis.

**9. DATA MANAGEMENT AND SOFTWARE/TOOLS****9.1 Software/Tools**

SAS® Version 9.4 or higher will be used for all analyses.

**9.2 Handling of Missing Values**

All patient discontinuations will be documented and the reason for discontinuation will be recorded.

In general, it is not planned to impute missing values. Exceptions are detailed in the subsequent subsections.

**9.2.1 Change from baseline endpoints**

The statistical Mixed effect Model for Repeated Measures (MMRM) used for the analysis of continuous secondary endpoints allows for form-level missing data, assuming they are missing at random. Item-level data for the PRO measures will be handled according to the instructions provided by the instrument developer.

**9.2.2 L-PF**

The L-PF scores represent means. Missing items are generally not counted in the denominator. Please note the following exception for the Dyspnea score items 1, 2, 4 – 10 and 12:

- If “No” is ticked and neither “A \*” nor “B \*\*” is ticked, the item is counted as missing but the item does contribute to the denominator.
- If “No” is ticked and “B” is ticked, then the item is not scored and does not contribute to the denominator.

\* Answer A: Patient avoided the activity because it was too difficult.

\*\* Answer B: Does not apply because the patient did not want to or had no opportunity to do the activity.

If the missing items are  $\geq 50\%$  within a score, then the corresponding score is set to missing.

### 9.3 Handling of Inconsistencies in Data and Outliers

Not planned.

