## **9.2 SETTING**

In this NIS, data on the effect of a nintedanib in chronic fibrosing ILD with progressive phenotype in about 100 patients will be collected in routine clinical practice by ca. 20 specialists, experienced in treating ILD patients, (e. g. pulmonologists and rheumatologists) throughout Germany. Each investigator will include ca. 5 consecutive patients for whom the physician had decided on a nintedanib treatment before.

Per definition, non-interventional studies do not include any randomization. In this study, there will be no procedure outside routine clinical practice. Patients will be recruited for this study only after a physician's therapeutic decision to treat the individual patient with nintedanib.

For ethical and/or medical reasons, patients with contraindications (CI) to nintedanib according to SmPC, including pregnant or lactating women, current cancer patients, patients not willing to consent and patients being spouse or lateral relatives to the second degree or economically dependent from the investigator will be excluded.

All calculations for this study, including statistics and patient numbers, are based on the randomized clinical trial INBUILD. In order to be able to duplicate the most crucial design features, in this study nintedanib will solely be tested as a first and only antifibrotic treatment in PF-ILD patients, as it was in INBUILD. Therefore, in accordance with INBUILD trial design, patients must not have used or use any antifibrotic before or during this observational study apart from nintedanib.

This study is planned to observe patients for 12 months. Therefore, patients with a life expectancy of 12 months or less should not be included. As acute exacerbations severely impact life expectancy, patients with acute ILD exacerbations should not be included in the study.

Patients must not participate in a parallel interventional clinical trial for not to interfere with the study aims and outcomes.

The impact of excluding those patients seems low, as the number is expected to be minimal and patients with contraindications in any case would not be treated with nintedanib.

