## 9.5 STUDY SIZE

In the INBUILD trial, patient groups on placebo vs nintedanib therapy differed in both their loss of FVC and dyspnea and cough symptom scores in the L-PF questionnaire (Figure 9.5:1; see below).

[figure not shown]

Figure 9.5:1 Changes from baseline to week 52 in L-PF symptoms dyspnea (left) and cough (right), domain scores respectively, seen in INBUILD

$\Delta$ FVC,  $\Delta$ dyspnea and  $\Delta$ cough symptom scores from INBUILD (see Table 9.5:1 below) were applied to estimate sample sizes.

Correlations between the change from baseline to week 52 in FVC (both FVC in mL and FVC as % predicted) and the change from baseline to week 52 in both L-PF dyspnea symptom score and cough symptom score measured by Pearson's correlation coefficient were  $\rho \approx -0.3$  in the Nintedanib arm of the treated set (see Table 9.5:1 below).

Table 9.5:1

Pearson correlation between the change from baseline to week 52 in FVC and the change from baseline to week 52 in L-PF symptoms scores in the Nintedanib arm (results were similar for the total population.)

Pearson correlation (change from baseline at week 52) between FVC and L-PF symptoms	Coefficient	95% Confidence interval	
		Lower	Upper
L-PF symptoms dyspnoe score and ...			
FVC in ml	-0.35	-0.45	-0.23
FVC (% predicted)	-0.37	-0.47	-0.26
L-PF symptoms cough score and ...			
FVC in ml	-0.26	-0.37	-0.14
FVC (% predicted)	-0.26	-0.37	-0.14

Currently, a meaningful threshold (“MCID”) has been published for neither the cough nor the dyspnea domain of the L-PF. However, should that information become available during the study, study results will be discussed in relation to meaningful thresholds (“MCID”) values.

Given a correlation  $\rho$  between change from baseline to week 52 in FVC [% pred.] and change from baseline to week 52 in dyspnea symptom score as well as change from baseline to week 52 in FVC [% pred.] and change from baseline to week 52 in cough symptom score of approximately -0.3, then 84 patient data sets would be required for evaluation. Assuming an estimated drop-out rate of approx. 15 % 100 patients will have to be recruited for this study. With this patient number (N = 84) and the assumption of a Pearson correlation of -0.3, the overall type I error is protected at the two-sided 0.05 level with a power of 80 %.

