**Pregnancy:**

In rare cases, pregnancy might occur in a NIS. Once a patient has been enrolled in the study and has taken study medication, the investigator must report any drug exposure during pregnancy in a study participant within 7 days by means of Part A of the Pregnancy Monitoring Form to the sponsor's unique entry point.

The outcome of the pregnancy associated with the drug exposure during pregnancy must be followed up and reported to the sponsor's unique entry point on the Pregnancy Monitoring Form (Part B).

The ISF will contain the Pregnancy Monitoring Form (Part A and B). As pregnancy itself is not to be reported as an AE, in the absence of an accompanying serious ADR and/or AESI, only the Pregnancy Monitoring Form and not the NIS AE form is to be completed. If there is a serious ADR and/or AESI associated with the pregnancy a NIS AE form must be completed in addition.

The following must be collected by the investigator in the (e)CRF from signing the informed consent onwards until the end of the study:

all adverse drug reactions (ADRs) (serious and non-serious),  
all AEs with fatal outcome,  
all AESIs

All ADRs and AESIs, including those persisting after study completion must be followed up until they are resolved, have been sufficiently characterized, or no further information can be obtained.

Expedited Reporting of AEs and Drug Exposure during Pregnancy to BI Pharmacovigilance

The following must be reported by the investigator on the NIS AE form and/or Pregnancy Monitoring Form from signing the informed consent onwards until the end of the study and provide o BI unique entry point:

All serious ADRs associated with the studied medical product nintedanib	immediately within 24 hours
All AEs with fatal outcome in patients exposed to studied medical product nintedanib	immediately within 24 hours
All protocol specified AESIs	Immediately within 24 hours
All non-serious ADRs associated with the studied medical product nintedanib	7 calendar days
Drug exposure during pregnancy	7 calendar days

The same timelines apply if follow-up information becomes available for the respective events. In specific occasions the Investigator could inform the Sponsor upfront via telephone. This does not replace the requirement to complete and fax the NIS AE form.

Information required

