## 10.1 Main analysis

Due to the observational nature of the study, all analyses are exploratory. No weighting will be applied to either of the co-primary endpoints.

For the analysis of the primary outcomes

- Correlation between change from baseline to week 52 in FVC [% pred.] and change from baseline to week 52 in dyspnea symptom score
- Correlation between change from baseline to week 52 in FVC [% pred.] and change from baseline to week 52 in cough symptom score

Pearson measures of correlation along with 95% two-sided confidence intervals and the two-sided p-values will be provided.

For the secondary outcomes

[figure not shown]
- Correlation between change from baseline to week 52 in FVC [mL] and change from baseline to week 52 in dyspnea symptom score
- Correlation between change from baseline to week 52 in FVC [mL] and change from baseline to week 52 in cough symptom score

Pearson measures of correlation along with 95% two-sided confidence intervals and the two-sided p-values will be provided.

The secondary outcomes

- absolute change from baseline in L-PF symptoms dyspnoea domain score between week 52 and baseline
- absolute change from baseline in L-PF symptoms cough domain score between week 52 and baseline

will be analyzed using a restricted maximum likelihood (REML) based repeated measures approach. Analyses will include the fixed, categorical effect of visit, as well as the continuous, fixed covariates of baseline and baseline-by-visit interaction. An unstructured (co)variance structure will be used to model the within-patient measurements.

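### Both co-primary correlations rest on Pearson's r with no visible outlier, rank-based or influence check, so a few patients with large joint changes at week 52 could inflate the result unnoticed

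*SAP*

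**What the plan says.** **Analysis.** For each co-primary outcome (change in FVC % predicted against change in L-PF dyspnea score, and against change in cough score), SAP 10.1 states: "Pearson measures of correlation along with 95% two-sided confidence intervals and the two-sided p-values will be provided". The two secondary correlations with FVC in mL are treated the same way. SAP 9.3, "Handling of Inconsistencies in Data and Outliers", says only that nothing is planned.

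**Sensitivity analyses.** SAP 10 adds two: a repeat without time windowing, and a per-protocol set if at least 10% of the treated set is omitted. The listed protocol deviations concern long interruption, another antifibrotic, and missing data. A patient who is acutely ill at week 52 but has complete data is not removed by any of them.

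**Event collection.** Protocol 11.2 requires the eCRF to hold "all adverse drug reactions (ADRs) (serious and non-serious"), all fatal AEs and all AESIs. Protocol 11.1 limits AESIs to gastrointestinal perforation and hepatic injury. Other AEs stay in the site's patient files.

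**Exacerbations.** Protocol 9.2 says: "As acute exacerbations severely impact life expectancy, patients with acute ILD exacerbations should not be included in the study". Protocol 9.2.2 excludes any past exacerbation. The visible text does not say how an exacerbation during follow-up is treated in the analysis.

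**Not shown.** SAP 10.2, protocol 9.7.2 and 9.3.2.3, and the separate TechnicalSAP are not available. A rank correlation or a scatter plot may be planned in one of them.

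**The concern.** Pearson's r gives great weight to points that are extreme on both axes. An acute respiratory episode at the week-52 visit would push FVC down and the dyspnea and cough scores up together, which is the direction of the study hypothesis. If a few such patients carried the coefficient, a value near the planned -0.3 could be reported with little or no association in everyone else, and nothing in the visible output would show it.

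This bears on how the result is used. Protocol 10.3 hopes that symptom change may prove an early sign of progression and help to establish the questionnaire in practice. That reading is stronger if the association runs through the cohort than if it sits in a handful of patients.

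**Working it through.** **1. The plan's own figure.** Protocol 9.5 assumes a correlation "of approximately -0.3, then 84 patient data sets would be required for evaluation", "at the two-sided 0.05 level with a power of 80" percent. By Fisher's z, n = [(1.960 + 0.842)/atanh(0.3)]² + 3 = 84.9. With the usual bias correction, power at 84 is 80.0%; simulated power of the t-test is 80.1%. The figure reproduces. For 15% drop-out, 84/0.85 = 99, against 100 planned. At n = 84, p < 0.05 needs |r| of at least 0.215.

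**2. Model for influence.** Inputs from the documents: n = 84 and Pearson's r. Assumed, because the documents give no SDs and no rate of acute events: k patients are shifted by -a SD in FVC change and +b SD in score change, and the other 84 - k have zero correlation. With p = k/84,

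expected r = -p(1-p)ab / √{[1 + p(1-p)a²][1 + p(1-p)b²]}.

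For k = 4, p(1-p) = 0.0476 × 0.9524 = 0.04535.

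- a = b = 3: 0.04535 × 9 = 0.408, so r = -0.408/1.408 = -0.29.
- a = b = 2: 0.04535 × 4 = 0.181, so r = -0.181/1.181 = -0.15.

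**3. Simulation (n = 84, zero correlation in the rest).**

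| Shifted patients | Shift on both variables | Mean Pearson r (p < 0.05) | Mean Spearman rho (p < 0.05) |
|---|---|---|---|
| 1 | 3 SD | -0.10 (14%) | -0.03 (5%) |
| 4 | 2 SD | about -0.15 (29%) | -0.10 (13%) |
| 4 | 3 SD | -0.29 (79%) | -0.13 (19%) |
| 5 | 3 SD | -0.34 (90%) | -0.16 (28%) |
| 10 | 2 SD | -0.30 (81%) | -0.22 (54%) |

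Without the shifted patients, mean Pearson r is 0.

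**4. Patients needed for an expected r of -0.30.** Shifts of 2 and 2 SD: 11 of 84. Shifts of 3 and 2 SD: 7. Shifts of 3 and 3 SD: 5. Shifts of 4 and 3 SD: 4. Shifts of 4 and 4 SD: 3. One patient is not enough at any shift tried (r from -0.05 to -0.16).

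**5. What the added check costs when nothing is wrong.** With clean bivariate normal data and a true correlation of -0.3, Spearman averages -0.28 with about 75% power, against -0.30 and 80% for Pearson. The two then nearly agree, so a gap such as -0.29 against -0.13 would stand out. Spearman is resistant, not immune, as the last row of the table shows.

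**The case against.** The case against has real force.

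- **The stated question is not limited to chronic change.** Protocol 8 asks for the correlation of 52-week changes in treated patients. Falling FVC with worsening symptoms during an exacerbation may be true association. This stands: the issue is how widely the coefficient applies, not an error in it.
- **A reader might infer that a few acutely ill patients are likely to create the whole correlation.** The documents do not support that. It needs shifts of about 3 SD or more on both variables, at the week-52 visit itself, and no correlation in anyone else. A recovered episode has no such effect. Patients who die or lack week-52 data do not enter, and a 0 to 100 score limits the shift. Table 9.5:1 of the protocol gives correlations with FVC % predicted of -0.37 and -0.26 in the source trial's nintedanib arm, with both intervals excluding zero. That makes a zero background a worst case. A weak background does leave some exposure: at an assumed -0.15, four patients at 2 SD move mean r to -0.28 and raise significance from about a quarter to about three quarters of studies.
- **A reader might also infer that acute events go unrecorded.** That is too broad. Fatal and drug-related events are collected. Concomitant diseases and medication (V1 to V5) and reasons for dose changes may show others. The visible text links none of these to the primary outcome.
- **Absence is not proven,** because of the sections not shown.
- **All analyses are labelled exploratory.** True, but p-values are reported and the size was set for 80% power. The label makes one more descriptive estimate easier to add.

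**Conclusion.** The point holds as a cheap improvement, not as a flaw that invalidates the design. On the visible text, both co-primary results depend on a coefficient sensitive to joint extremes, and nothing planned would reveal that dependence. The size is conditional: four of 84 patients (about 5%) at 3 SD on both variables can bring r to -0.29 from no association elsewhere, while four at 2 SD reach only about -0.15. The shifts, the number of such patients and the zero background are assumptions. Without SDs or an event rate in the documents, vulnerability is shown and likelihood is not.

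**What to change.** Keep Pearson's r as the primary analysis. In SAP 9.3 and 10.1, pre-specify as a sensitivity analysis, for each primary and secondary correlation:

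1. Spearman's rho with a 95% CI, beside Pearson's r.
2. A scatter plot of the two changes.
3. A reporting sentence: if the two coefficients differ materially, the report says that the Pearson result depends on a few patients with extreme changes.

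Optionally, and for description only, show r with and without patients whose already collected concomitant-disease, medication or dose-change entries indicate an acute respiratory event near week 52. This selects on something that happens after baseline, so it should carry no decision rule.

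If the sections not shown already contain these outputs, a cross-reference in SAP 9.3 is enough.

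Two further steps may look natural but are not advised. Dropping the most influential one to five patients and requiring the result to persist would penalise a genuine effect: in clean data with a true correlation of -0.30, removing the five most supportive points cuts mean r to -0.14 and significance to 24%. A new eCRF field would mean retrospective collection at about 20 sites, with the SAP dated 17 November 2022 and data collection planned to end in February 2023.

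Cost: a few lines of SAP text and a few SAS statements, some extra exploratory estimates, and possibly a less favourable reading.

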## 10. DATA ANALYSIS

**Treated Set (TS):** All patients with signed informed consent who received at least one dose of nintedanib will be included in the treated set.

**Per Protocol Set (PPS):** All patients from the treated set who met all inclusion and exclusion criteria and did not violate any important protocol deviations.

Important protocol deviations:

- Dose interruption of nintedanib for more than 12 weeks and/or initiation of another antifibrotic therapy during the observation phase of the study.
- Missing patient questionnaires or other variables necessary for assessment of the primary study outcome
- Last patient visit completely missing (if no data is available for week 52)
- No FVC measurement available within 3 months prior to inclusion and FVC was not evaluated at baseline

All analyses will be performed on the treated set. Primary and secondary outcomes will be analysed for patients who have available data for the analysis of the efficacy endpoints. Additionally, all analyses for baseline and efficacy will be done on the per protocol set if  $\geq 10\%$  of the treated set is omitted.

All analyses on the treated and per protocol set will be performed using the method of time windowing: Only data will be used that was documented at performed visits within  $\pm 6$  weeks of the planned visit date (see 6.4 STUDY VISITS). For purpose of sensitivity primary and secondary endpoints will also be analysed without time windowing.

No subgroup analyses are planned due to the small number of patients.

For categorical variables summary tabulations of the number and percentage (%) relative to the treated set (unless otherwise specified, all patients in the patient set whether they have non-missing values or not) within each category of the parameter will be presented. The category missing will be displayed only if there are actually missing values.

For continuous variables number of values, mean, standard deviation, minimum, 25th percentile, median 75th percentile, maximum and number of missing values will be presented.

Percentages will be rounded to two decimal places.

No interim analysis is planned.

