#### Inclusion criteria

- Adults  $\geq$  18 years at Visit 1
- Subjects must be contractually capable and mentally able to understand and follow the instructions of the study personnel
- Physician's diagnosis of chronic fibrosing ILD with a progressive phenotype, except IPF
- Treatment with nintedanib in INREAL will be the first and only prescription of any antifibrotic treatment for each individual patient within this observational study after a physician's decision being made for this treatment option earlier
- Outpatients not currently hospitalized with a life expectancy  $>$  12 months per investigator's assessment
- Written informed consent prior to study participation
- Current FVC measurement (taken within the last 3 months) available in the patient file
- Women of childbearing potential must take appropriate precautions against getting pregnant during the intake of nintedanib.

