**9.2.3      Study visits**

In this NIS, data on the effect of a treatment with nintedanib on differences in cough and dyspnea scores, measured via the L-PF questionnaire, will be collected and this information will be assessed in relation to FVC from these patients' medical files in patients with chronic fibrosing ILD with a progressive phenotype.

Four visits are mandatory within this study:

V1 – baseline visit

V3 – mid-observation period

planned visit date: 26 weeks after V1

must not take place earlier than week 20 or later than week 32 after V1

V5 – end of observation

planned visit date: 52 weeks after V1, must not take place earlier than week 46 or later than week 58 after V1

V6 – Follow-up 52 weeks after start of treatment

Each of these visit should take place not earlier than six weeks before and not later than six weeks after the planned visit date (V1 + 26 weeks; V1 + 52 weeks) and thus reflect patients' and physicians' real-world experience.

In addition to Visits 1, 3 and 5 described here, optional study visits will be enabled between V1 and V3 as well as between V3 and V5, each occurring about midway between V1 and V2 or V2 and V3, respectively. Optional visits should take place

optional Visit V2: planned visit date week 13 after V1

if applicable, V2 must not take place earlier than week 7 or later than week 20 after V1

optional visit V4: planned visit date week 39 after V1

if applicable V4 must not take place earlier than week 33 or later than week 45 after V1

When optional visits are conducted, then the same parameters as in Visit 3 should be documented.

Therefore, patients will be seen by their investigator at least every 6 months and up to every quarter of the observational period.

The baseline visit will take the patients ca. one hour including filling out the questionnaires, visits 2 to 6 will take about 30 minutes each. All data documented during those visits, including the questionnaires, record examinations and information necessary during the course of the disease and nintedanib treatment.

If possible, patients who discontinue the study before week 52 for any reason should be contacted for survival status and follow-up data at week 52, as available (Visit 6). A phone contact with the patient / relatives / family doctor is acceptable for V6.

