So, the time needed by the patient for the whole study depends on the number of visits performed. The duration of each visit depends on the amount of data to be collected and the possible questions to be discussed between investigator and participant. For baseline, we

presume about one hour, for the following visits about 30 minutes including filling out the questionnaire.

All details on the data collected and tasks performed at each visit are shown in [table 9.2.3: 1](#).

Table 9.2.3: 1 Flow Chart

Parameter	Visit 1; baseline visit	Visit 2; (optional) ca. week 13	Visit 3; mid of observa- tion; ca. week 26*	Visit 4; (optional) ca. week 39	Visit 5; end of observa- tion; ca. week 52	Visit 6 FU ca. week 52**
Informed Consent	X					
Inclusion / Exclusion Criteria	X					
Patient demographics (age, gender, height, and weight)	X					
Smoking history	X					
History of ILD, including ILD entity and HRCT pattern (where available in patient documentation)		X				
current DLCO measures (where available in patient documentation)	X	X	X	X	X	
Concomitant diseases / Comorbidities	X	X	X	X	X	
Past ILD therapies (6 weeks before visit 1)	X					
Current ILD related or other relevant concomitant medication	X	X	X	X	X	
FVC (mL and % pred.; if available in patient data)	X	X	X	X	X	X
Severity of disease as per the treating physician's estimation (if available in patient data)	X	X	X	X	X	X
L-PF questionnaire, completed by patient	X	X	X	X	X	X

Table 9.2.3: 1 (cont'd)

Flow Chart

Parameter	Visit 1; baseline visit	Visit 2; (optional) ca. week 13	Visit 3; mid of observa- tion; ca. week 26*	Visit 4; (optional) ca. week 39	Visit 5; end of observa- tion; ca. week 52	Visit 6 FU ca. week 52**
Safety: Adverse Drug Reactions (serious and non-serious), fatal AEs, pregnancy	X	X	X	X	X	X
Rationale for treatment discontinuation (if applicable)		X	X	X	X	
Further treatment options yes/no (as applicable)		X	X	X	X	X
Intention to continue or discontinue treatment with nintedanib after the study (yes/no)		X	X	X	X	
Survival data						X

\* after 26 weeks of observation for each individual patient

\*\* if available and/or patients willing to perform, phone contact acceptable

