### **9.3 VARIABLES**

The following parameters will be collected and assessed at visits 1 to 5, as applicable:

- Patient demographics (age, gender, height, weight)
- Smoking history, current status (current smokers, former smokers, and never smokers) and pack-years
- History of ILD, including ILD entity and HRCT pattern (where available in patient documentation)
- current DLCO measures (where available in patient documentation)
- Concomitant diseases
- Previous ILD therapies in the 6 weeks before visit 1
- Current ILD related or other relevant concomitant medication
- FVC (mL and % pred.; if available in patient data)
- Severity of disease as per the treating physician's estimation (if available in patient data)
- L-PF questionnaire, completed by patient
- Safety: ADRs (serious and non-serious), fatal AEs, pregnancies during the study
- Rationale for treatment discontinuation (if applicable)
- Intention to continue or discontinue treatment with nintedanib (Ofev®) after the study (yes/no)
- Further treatment options yes/no, as applicable

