## 6.4 STUDY VISITS

In this NIS, data on the effect of a treatment with nintedanib on differences in cough and dyspnea scores, measured via the L-PF questionnaire, will be collected and this information will be assessed in relation to FVC from these patients' medical files in patients with chronic fibrosing ILD with a progressive phenotype.

Four visits are mandatory within this study. In addition to Visits 1, 3 and 5 optional study visits will be enabled. Each of these visits should take place not earlier than six weeks before and not later than six weeks after the planned visit date:

V1 – baseline visit

V3 – 26 weeks after V1 (20 – 32 weeks)

V5/V6 – 52 weeks after V1 (46 – 58 weeks)

Optional visits should take place:

V2 – 13 weeks after V1 (7 – 20 weeks)

V4 – 39 weeks after V1 (33 – 45 weeks)

If possible, patients who discontinue the study before week 52 for any reason should be contacted for survival status and follow-up data at week 52, as available (Visit 6).

The patients have the right to stop study participation any time and for any reason, without any drawback on their further treatment. Study participation may be stopped for a given patient in case of individual safety issues.

For more details on study visits please see section 9.2.3 of the Study Protocol.

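### Should the analysis window be applied to the date of the FVC measurement rather than to the visit at which it was documented?

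*SAP*

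**What the plan says.** The primary outcomes are Pearson correlations between the 52-week change in FVC [% pred.] and the 52-week change in the L-PF dyspnea and cough scores (Protocol 9.3.2.1, SAP 7.2.1). SAP 10 applies a time window to all analyses: "Only data will be used that was documented at performed visits within" six weeks of the planned visit date. Primary and secondary endpoints are repeated without the window as a sensitivity analysis.

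The two measures reach the database by different routes. Protocol 9.3.2 has the L-PF completed during the visit and reflecting that day. Protocol 9.2.3 says the scores are "assessed in relation to FVC from these patients' medical files", the flow chart asks for FVC only where available, and Protocol 10.4 requires no examination beyond routine care. Protocol 9.3 says "The following parameters will be collected and assessed at visits 1 to 5, as applicable".

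At baseline, the inclusion criterion is "Current FVC measurement (taken within the last 3 months) available in the patient file". The matching important protocol deviation in SAP 10 is "No FVC measurement available within 3 months prior to inclusion and FVC was not evaluated at baseline".

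At week 52, SAP 6.4 gives V5 and V6 one window, weeks 46 to 58. Protocol 9.2.3 adds: "A phone contact with the patient / relatives / family doctor is acceptable for V6".

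**The concern.** For the questionnaire, the visit date and the measurement date are the same. For FVC nothing in the two documents makes them so. A file value up to three months old appears usable as baseline, which would put untreated time into the FVC change but not into the L-PF change. At week 52 no limit on the age of the FVC is stated, and a value recorded at a telephone V6 must have been measured on another occasion.

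The primary result would then correlate changes over unequal periods, and the report would not show how often. The unwindowed sensitivity analysis would not reveal it either, because it relaxes the visit window and makes no use of FVC dates.

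**Working it through.** **The plan's own figure.** Protocol 9.5: correlation -0.3, two-sided 0.05, 80% power, 84 evaluable, 100 recruited. Fisher z: n = ((1.960 + 0.842)/atanh 0.30)² + 3 = 84.9. Power at n = 84 is 79.6% (80.0% with the t-based critical value). Drop-out: 84/0.85 = 98.8, so 99, consistent with 100. The sampling 95% interval at -0.30 and n = 84 is tanh(-0.3095 ± 1.960/√81) = -0.48 to -0.09.

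**How far the periods can differ.** With V5 at week 52 the L-PF change covers 52 weeks. With a baseline FVC 13 weeks old, the FVC change covers 52 + 13 = 65 weeks.

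**Model.** Let g be the weeks by which the baseline FVC precedes V1, h the weeks by which the last FVC precedes the last L-PF, and m the measurement-error share of the FVC-change variance (taken as 0 or 0.5). Assume an aligned correlation of -0.30 and FVC age unrelated to disease course, and work with deviations from the mean decline.

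- Irregular decline (independent increments): r = -0.30 × (1 - E[h]/52) / √(m + (1-m)(52 + E[g] - E[h])/52)
- Steady slopes, with k = (52 + g - h)/52: r = -0.30 × E[k] / √((1-m)E[k²] + m)

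Worked case: h = 13 in half of patients, so E[h] = 6.5; irregular, m = 0.5. r = -0.30 × 0.875/√(0.5 + 0.5 × 0.875) = -0.2625/0.9682 = -0.271.

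| FVC age and share of patients | Range of r over both models and both m |
|---|---|
| Baseline, 0–13 weeks evenly spread, half | -0.291 to -0.308 |
| Baseline, 13 weeks, half | -0.283 to -0.316 |
| Week 52, 13 weeks, half | -0.271 to -0.297 (power 71–79%) |
| Baseline, 13 weeks, all | -0.268 to -0.331 |
| Week 52, 13 weeks, all | -0.241 to -0.300 (power 60–80%) |
| Both ends, 13 weeks, all | -0.225 to -0.300 |

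The all-patient rows are outer bounds that nothing in the documents supports. In the other rows the largest shift is 0.029. An old baseline value can move the correlation either way.

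**The telephone visit.** Protocol 9.2.3 separates V6 from V5 only for patients who leave the study early; for everyone else the two are one visit. Protocol 9.4 and SAP 8 plan the paper L-PF for V1 to V5, although the flow chart also ticks it at V6. Where no L-PF is obtained there is no pair, and the available-data rule in SAP 10 removes the patient.

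It would be wrong to apply the 15% drop-out share to the 84, because 84 is already net of drop-out. If the leavers did supply pairs, n would be about 99. With those 15 of 99 carrying a 13-week-old FVC, r is -0.291 to -0.299 and power about 84–86%. Without them, n is 84 and power about 80%.

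**What re-windowing would do.** Suppose a window on the spirometry date removes 10 of the 84 patients. Power at -0.30 and n = 74 is 74.2%. Now keep those 10 with a 13-week-old last FVC. In the least favourable model E[h] = 130/84 = 1.55, and r = -0.30 × 0.9702/√(0.5 + 0.5 × 0.9702) = -0.293, with power about 78% at n = 84. A week 46–58 window on the FVC date would still admit an FVC at week 46 paired with an L-PF at week 58, a gap of 12 weeks.

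**A closely paired subset.** At an assumed n = 60 the 95% interval around -0.30 is -0.51 to -0.05, too wide to tell -0.27 from -0.33.

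**The case for a change.** The best case for acting is that a rule deciding which data enter the primary analysis belongs in the SAP, that the outcome is framed as change over 52 weeks of treatment, and that adding visit windows in SAP 2.1 shows the sponsor thought timing mattered. The statement that parameters are collected at visits 1 to 5 does not settle the point, since the same list includes smoking history and past therapies. The share of patients with mismatched dates is unknown, and no output described in the two documents would show it.

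Much of this stands. The text does not fix the FVC date, and same-day spirometry is a plausible reading but not a stated requirement. The eCRF specification, data validation plan and table shells were not available, so whether FVC dates are recorded or checked is unknown. What does not follow is that the analysis as planned would mislead. The age limit that the documents do state, three months at baseline, gives a small shift with no consistent direction, and the week-52 route through a telephone V6 is confined to early leavers who may have no L-PF to pair.

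**Conclusion.** No change to the plan is needed. The documents leave the dating of FVC to the analyst, and the sensible choices are close at hand: the pre-treatment value nearest V1 within the permitted three months, and the value recorded with the week-52 visit. If FVC dates are already in the database, the gap to the L-PF date can be described in the report. The disagreement over whether the L-PF is collected at V6 is a clerical inconsistency.

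With up to half of patients affected at one end by up to 13 weeks, the expected correlation moves by at most about 0.03. That is small beside a sampling interval of -0.48 to -0.09, and beside the 0.11 between the two INBUILD values behind the planning assumption (-0.37 for dyspnea, -0.26 for cough, both with FVC % predicted). All analyses are declared exploratory. A stricter window would discard primary data, lower power and still allow a 12-week mismatch.

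This rests on the two decline models, the two measurement-error shares, and FVC age being unrelated to disease course. The frequency of mismatched dates is an assumption. If nearly all patients had old values at week 52 or at both ends, the shift could reach 0.06 to 0.075, but nothing in the documents points to that.
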